1 INTRODUCTION

1.1 Disease Background

Duchenne muscular dystrophy (DMD) is a fatal, progressive, genetic neuromuscular disease that affects approximately one in 5,000 males born worldwide; it is the most common type of childhood muscular dystrophy¹⁻³. Patients with DMD typically present with initial symptoms around 2.5 years of age and are diagnosed at approximately 5 years of age⁴. Progressive muscle degeneration eventually leads to loss of ambulation in most patients by 10 to 12 years of age^{5, 6, 7}. As the disease progresses, DMD patients develop respiratory, orthopedic, and cardiac complications⁶⁻⁸. In the absence of an intervention, patients typically die from respiratory failure or cardiac complications in their mid-20's^{9, 10}. With supportive care, such as corticosteroid use, ventilatory assistance, and scoliosis surgery, life expectancy in DMD patients may be extended to approximately 30 years of age¹¹.

Duchenne muscular dystrophy is an X-linked genetic disorder caused by mutations in the dystrophin-encoding *DMD* gene^{12, 13}. Normal dystrophin protein is part of a protein complex called the dystrophin-glycoprotein complex, which provides structural stability to skeletal muscle and protects the muscle from injury during contraction and relaxation^{14, 15}. In addition, dystrophin is essential for cell survival via a transmembrane signaling function and modulation of vasomotor response to physical activity¹⁵. Mutations in the form of large deletions (one or more exons) account for approximately two-thirds of all *DMD* mutations; the remaining mutations are due to duplications and small deletions, insertions, point mutations, or splicing mutations¹⁶. Deletions, which are typically clustered in a hotspot region between exons 45 and 55, disrupt the open reading frame and prevent translation of dystrophin¹⁷. Mutations in the *DMD* gene that are amenable to exon 51 skipping occur in approximately 13% of patients with DMD¹⁸, the population that might benefit from exon 51 skipping ASOs. These patients might potentially benefit from WVE-210201. Absent or defective dystrophin protein, resulting from *DMD* gene mutations, disrupts the dystrophin glycoprotein complex, leading to increased muscle membrane fragility, chronic muscle damage, inflammation, replacement of muscle fibers with fat and fibrotic tissue, and then loss of muscle function^{6, 7, 19}.

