4.3 Study Endpoints

4.3.1 Double-blind Treatment Period

Study Endpoints: The primary and key secondary efficacy endpoints differ by region. All other endpoints are the same across regions.

Primary Efficacy Endpoint

- Change from baseline in dystrophin level (% normal dystrophin) assessed by Western blot of muscle tissue (United States/Other regions, as applicable)
- Change from baseline in North Star Ambulatory Assessment (NSAA) through 48 weeks (EU/Japan)

Secondary Efficacy Endpoints

- Key secondary endpoint - Change from baseline in NSAA through 48 weeks (United States/Other regions, as applicable)
- Key secondary endpoint - Change from baseline dystrophin level (% normal dystrophin) assessed by Western blot of muscle tissue (EU/Japan)
- Change from baseline in upper limb proximal strength assessed by hand held myometry through 48 weeks
- Change from baseline in 4-stair climb (4SC) through 48 weeks
- Change from baseline in the 10-meter walk/run test through 48 weeks

- Change from baseline in forced vital capacity (FVC; % predicted) through 48 weeks
- Change from baseline in the 95th percentile of stride velocity through 48 weeks

Exploratory Efficacy Endpoints

- Change from baseline in Pediatric Quality of Life Inventory (PedsQLTM)-neuromuscular module at 48 weeks
- Change from baseline in Pediatric Quality of Life Inventory (PedsQLTM)-Generic Core Scale module at 48 weeks
- Change from baseline in individual NSAA items through 48 weeks
- Change from baseline in respiratory function (peak flow rate [PFR], cough peak flow [CPF]) through 48 weeks
- Change from baseline in PUL 2.0 through 48 weeks
- Time to milestone events (loss of ambulation, loss of self-feeding, requirement of daytime ventilation on a regular basis)
- Changes from baseline in daily activity as measured by a wearable device measure

Safety, Pharmacokinetic and Pharmacodynamic Endpoints

- Adverse events, laboratory values, physical exams and vital signs
- Changes from baseline in cardiac functions by ECHO
- Concentration of WVE-210201 in plasma
- Concentration of WVE-210201 in muscle
- Exon-skipping by RT-PCR in muscle tissue
- Dystrophin localization by immunofluorescence

4.3.2 *Open-label Treatment Period*

- Long-term efficacy, safety, and PK of WVE-210201

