5.1 Inclusion Criteria

1. Patient and/or parent or legal guardian must have the ability and be willing to provide written informed consent prior to any study-related procedures
2. Diagnosis of DMD based on clinical phenotype with increased serum creatine kinase
3. Documented mutation in the Dystrophin gene associated with DMD that is amenable to exon 51 skipping
4. Ambulatory male, able to walk independently for at least 10 meters in 10 seconds or less at the time of Screening visit (performed as part of the NSAA)
5. Age of ≥ 5 and ≤ 12 years at time of randomization
6. Willing and able to comply with scheduled visits, drug administration plan, laboratory tests, study restrictions, and all study procedures, including undergoing the biopsy procedures
7. Stable pulmonary and cardiac function, as measured by:
 - a. Reproducible percent predicted forced vital capacity (FVC) $\geq 50\%$
 - b. Left ventricular ejection fraction (LVEF) $>55\%$ in patients <10 years of age and $>45\%$ in patients ≥ 10 years of age, as measured (and documented) by echocardiogram
8. Currently on a stable corticosteroid therapy regimen, defined as initiation of systemic corticosteroid therapy occurred ≥ 6 months prior to Screening, and no changes in dosing ≤ 3 months prior to Screening visit
9. Adequate deltoid muscle at Screening to perform open muscle biopsies
10. Sexually mature males must be willing to use contraception for the duration of the study, if the patient is sexually active
11. Patient and caregivers must agree not to post any study-related information on social media

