11.3.2.2 Analysis of North Star Ambulatory Assessment (NSAA)

Another primary objective is to evaluate the efficacy of WVE-210201 by assessing changes in the NSAA. Therefore, the primary efficacy endpoint for the EU and Japan and the key secondary endpoint for the United States and Other regions is the change in NSAA from baseline over 48 weeks. The treatment policy estimand which assesses the effect of treatment initially assigned at baseline (regardless of adherence to the planned course of treatment) will be used. The analysis population will be the ITT population. The main estimator will be a Bayesian progression model (BPM) to compare the change in NSAA between patients treated with WVE-210201 and placebo treated patients^{59,60}. The placebo data from this study will be augmented with historical control data via a Bayesian meta-analytic approach.

The BPM assumes a non-parametric rate of progression of the NSAA for placebo patients and a proportional rate of slowing NSAA progression for the treated patients relative to the placebo patients at each time point. The model will include covariate effects to measure differences in the rates of progression based on patient-specific baseline covariates. Additionally, random patient variability will be accounted for using patient-level random effects of the rate of NSAA progression. Borrowing from historical control data to augment the placebo arm information will entail including a random data source effect to model the between-source variability in NSAA progression rates.

The NSAA analysis will be independent of the dystrophin analysis described in [Section 11.3.2.1](#). Let the NSAA at visit j for patient i be Y_{ij} , for $j = 0, \dots, 4$ and $i = 1, \dots, n$. The Y_{i0} observation corresponds to the baseline visit. Visits $j = 1, 2, 3, 4$ refer to the post-baseline visits (each separated by 12 weeks). Let X_i be a vector of dimension C of baseline covariates for patient i that have been standardized. The DPM is

$$Y_{ij} = \gamma_i + \exp(\theta_{t(i)} + \eta_i + \alpha X_i + \delta_{s(i)}) \sum_{k=0:j} \beta_k + \epsilon_{ij}; \\ \epsilon_{ij} \sim N(0, \sigma_{t(i),s(i)}^2).$$

Patient-specific random effects, $\gamma_i, i = 1, \dots, n$, represent the patient-specific mean NSAA at the time of randomization.

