It is assumed that $\beta_0 = 0$ and the decline in NSAA per each 12-week period for a placebo patient in this study with average baseline covariates is modelled as $\beta_k, k = 1, \dots, 4$, with the sum of all β_k equal to the total decline over 48 weeks. Each β_k is assumed to be less than or equal to zero to ensure a monotonic decline.

For patient i , the treatment arm is labelled $t(i)$ with 0 for placebo, 1 for WVE-210201 3 mg/kg and 2 for WVE-210201 4.5 mg/kg. The disease rate ratio (DRR) for treatment T is the parameter $\exp(\theta_T), T = 0, 1, 2$. For a placebo-treated patient, the DRR is assumed to be 1 ($\theta_0 = 0$). Thus, the DRR parameter for treatment T represents the multiplicative change to the mean decline of a placebo-treated patient. If the DRR is less than 1, the rate of decline for treatment T is slower than placebo; the DRR value represents the proportional slowing of NSAA progression. For example, a DRR = 0.75 corresponds to a 25% slowing in the rate of NSAA progression. The WVE-210201 treatment arms will be pooled for the NSAA analysis and the restriction that $\theta_1 = \theta_2$ incorporated into the DPM. However, if the randomization to the WVE-210201 3 mg/kg arm is stopped after an interim analysis (Section 11.5), the WVE-210201 treatment arms will not be pooled. Summaries of the posterior distribution for the DRR ($\exp(\theta_T)$) for each arm will be provided including the probability that each treatment is superior to placebo, $Pr(\exp(\theta_T) < 1)$, as well the mean and 95% credible intervals for each DRR.

Patient-specific multiplicative random effects in the slope, $\exp(\eta_i), i = 1, \dots, n$, represent the patient-specific proportional increase or decrease in the rate of progression. Covariate effects are modelled as $\alpha_c, c = 1, \dots, C$, and account for explained variability in the rate of NSAA progression due to subject-specific baseline covariates.

Random data source effects to account for the between-source variability in NSAA progression rates are modelled as $\delta_{s(i)}$, where the source of each patient is labelled $s(i)$ with 0 for this study and 1:S for the historical data sources. These source effects account for the variability in the rate of progression of NSAA between placebo and historical controls in the different data sources that are not explained by baseline covariates. For a patient randomized in this study, the source effect is assumed to be 1 ($\delta_0 = 0$).

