The residual errors for the individual observations, $\epsilon_{ij}, i = 1, \dots, n$ and $j = 0, \dots, 4$, are modelled as independent normal distributions with a treatment arm and source-specific standard deviation of $\sigma_{t(i),s(i)}$.

Missing NSAA data can result from intercurrent events which include discontinuation of the study and loss of ability to complete any NSAA activities. With the selected primary estimand, missing NSAA assessments or NSAA assessments collected after randomized therapy discontinuation will be imputed using a control-based imputation strategy for treated patients. Placebo patients will have missing observations imputed assuming MAR. The loss of the ability

to complete any NSAA activities will be recorded as 0 on the case report forms and used in the analysis.

The posterior probability that the DRR is less than 1 will be assessed to determine significance of the WVE-210201 NSAA treatment effect. Superiority on slowing the rate of decline on NSAA will be declared if the posterior probability that either 1) the pooled WVE-210201 treatment effect ($\theta_1 = \theta_2$; if the low dose has not been dropped) or 2) the WVE-210201 treatment effect θ_2 (if randomization to the WVE-210201 3 mg/kg has been stopped) is superior to placebo and slows the rate of NSAA progression is greater than 0.975:

$$\Pr(\exp(\theta_2) < 1) > 0.975.$$

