11.3.2.3 Secondary Efficacy Analyses

The secondary efficacy endpoints will be analyzed in the ITT population using a Bayesian progression model analogous to the model described for the analysis of the NSAA endpoint.

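### FVC % predicted and hand-held myometry are assigned a model that can only express slowing of a decline, with no placebo decline quantified for either; an additive model is a cheap safeguard

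*Combined protocol and SAP*

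**What the plan says.** Section 11.3.2.3, like the synopsis, gives one sentence for all secondary endpoints other than dystrophin and NSAA: they are analysed "using a Bayesian progression model analogous to the model described for the analysis of the NSAA endpoint". Two of the five listed in Section 4.3.1 are FVC % predicted and myometry ("Change from baseline in upper limb proximal strength assessed by hand held myometry through 48 weeks").

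The parent model in Section 11.3.2.2 is, with baseline random effect γ and error ε,

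Y_ij = γ_i + exp(θ + η_i + αX_i + δ) · Σβ_k + ε_ij.

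- Each β_k "is assumed to be less than or equal to zero to ensure a monotonic decline".
- The DRR, exp(θ), "represents the multiplicative change to the mean decline of a placebo-treated patient", and the model assumes "a proportional rate of slowing NSAA progression for the treated patients relative to the placebo patients".
- Superiority is claimed if the posterior probability that treatment "is superior to placebo and slows the rate of NSAA progression is greater than 0.975". That rule is written for NSAA only.

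Section 11.1 quantifies a placebo course for NSAA alone: an average decline of 3 points in a year. Sections 1.1 and 2 describe weakening muscle in DMD, and corticosteroids slowing that loss, without a rate for myometry. No section gives a 48-week course for FVC % predicted. Section 11.3.3 limits family-wise error control to the primary and key secondary comparisons.

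**The concern.** A ratio of declines is informative only where there is a decline to divide by. Every factor multiplying Σβ_k is positive, so neither an arm nor a single boy can have a fitted gain. If the placebo arm is flat or improves on FVC % predicted or myometry, the DRR has nothing to measure, and a true gain on drug lies outside the model.

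Upper limb strength and respiratory function are both named secondary objectives in Section 3.1. At stake are their estimates, credible intervals and probabilities of superiority.

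**Working it through.** **1. The plan's own figure.** The only power statement for a functional endpoint is NSAA: difference 3.0, SD 4.5, 10% dropout, two-sided 5%, 150 patients. One dose against pooled placebo is 45 v 45 after dropout: 3 / (4.5·√(2/45)) = 3/0.949 = 3.16, and Φ(3.16 − 1.96) = 88.5% (87.9% by the t-test). This reproduces the stated 88%. With doses pooled, as the NSAA analysis does, 90 v 45 gives 3 / (4.5·√(1/90 + 1/45)) = 3.65 and Φ(1.69) = 95.5%. No SD, effect or power is given for FVC or myometry.

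**2. The ceiling on benefit.** If placebo declines by D, the treated decline is DRR × D, which is above zero, so the largest benefit the model can hold is just under D. For NSAA, D is about 3 and the planned difference of 3 uses all of it (DRR = 0/3 = 0). For FVC and myometry D is not stated; at D = 0 the ceiling is 0.

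**3. Why the DRR drifts below 1.** Reduce the model to two arm means: placebo B ≤ 0, treated exp(θ)·B. If the observed treated mean is zero or above, its distance from exp(θ)·B grows with θ for every B < 0. The likelihood therefore favours lower θ whatever placebo did, and with a θ prior centred at 0 and independent of B the posterior median DRR is below 1. On an SD of 4.5 with 90 treated boys, the standard error is 4.5/√90 = 0.47. A true mean of +1.5 is then 3.2 standard errors above zero, so this happens almost always.

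**4. Simulation A.** Assumptions, not from the documents: NSAA's SD of 4.5 borrowed; 45 placebo v 90 pooled active; placebo change 0 or +1.5 (0.33 SD); true benefit 0 or +3 (0.67 SD); all priors. The 0.975 rule is borrowed from NSAA. Cells show placebo flat / placebo +1.5.

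| Model and prior | Median DRR, no effect | Success, no effect | Success, benefit +3 |
|---|---|---|---|
| Two means, θ SD 0.5 | 0.85 / 0.86 | 0–1% | not reported |
| Two means, θ SD 1 | 0.63 / 0.59 | 0–1% | 0% / 0% |
| Two means, θ SD 2 | 0.33 / 0.25 | 0–1% | 7% / 0% |
| Two means, θ SD 10 | about 0 | 19% / 16% | 99% / 97% |
| Four visits, θ SD 1, prior on total decline | 0.73 / 0.59 | 3% / 0% | 10% / 1% |
| Four visits, θ SD 1, independent half-normal steps, SD 0.75 | 0.46 / 0.26 | 21% / 38% | 100% / 94% |
| Additive difference in means | n/a | about 2.5% | about 95% |

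With placebo declining by 3, the four-visit model gave a null DRR of 0.91–0.96, false success 5% (100 runs; Monte Carlo SE √(0.05·0.95/100) = 2.2 points) and power 98–100%. A rougher set of 40 runs with wider independent step priors (SD 5, θ SD 1) reached about 40% false success at either placebo trend; the same setting gave 10% with placebo declining.

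**5. Two further simulations.** Both use change SD 1, 45 v 90, benefit 0.5 SD. The additive benchmark by formula is Φ(0.5/√(1/90 + 1/45) − 1.96) = Φ(0.78) = 78%.

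- B (normal patient slopes, θ prior SD 1 or 3): flat placebo gave a null median DRR of 0.85, error 1.5–4.5% and power 73–89%. Placebo at +0.4 SD gave DRR 0.31–0.51, error 6.6–18% and power 26–53%. The additive comparison had about 80% throughout.
- C: the ratio model had 68–83% power with placebo declining and 18–25% at +0.4 SD. The null median DRR was 0.67–0.82 with placebo flat or rising. The additive comparison had 74–82% whatever the trend.

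**6. Dropping only the sign restriction.** With placebo +1.5 and benefit +3, the treated mean is +4.5 and the raw ratio is 4.5/1.5 = 3. The run gave a DRR of about 2.4 and 0% success: a larger gain is scored as faster progression.

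**The case against.** The case against is substantial.

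- The text says the secondary model is analogous, not identical. A literal copy cannot be meant for the 4-stair climb, which is timed (Section 8.7.2.2) and worsens upward, so some adaptation is implied.
- A reader might infer from "Stable pulmonary and cardiac function, as measured by" that FVC is expected to be flat. It is an entry level (reproducible FVC of at least 50% predicted, plus an LVEF limit), not a 48-week course. Likewise "As the disease progresses, DMD patients develop respiratory, orthopedic, and cardiac complications" says nothing about the trend in FVC % predicted at ages 5 to 12, and scaling to predicted values means growth in raw volume is no evidence of gain.
- A reader might also infer that no decline in strength is described. Sections 1.1 and 2 do describe one; they give no rate.
- These endpoints have no success threshold, power or type I role. With a flat placebo, simulation B was close to nominal. Simulations A and B omit baseline covariates.

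All of this stands, and it rules out calling the plan wrong as written. Two replies do not remove the point. An unstated adaptation is not a prespecified one: Sections 11.5.1 and 11.5.2 send thresholds, enrolment targets and the target DRR to the SAP, not the form of the secondary model. And a sentence relaxing the sign restriction would leave the ratio scale, which fails on its own (step 6).

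**Conclusion.** This is a worthwhile low-cost improvement, with conditional harm. The documents support a decline-only ratio model for NSAA. For FVC % predicted and myometry they give no rate of placebo decline to support it. If placebo boys decline clearly, the model serves. If they are flat or improve, the DRR is biased below 1 under no effect (median about 0 to 0.86 across the settings run) and a gain on drug cannot be represented.

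The size of any decision error cannot be attributed to this plan. In the table, false success ran from 0% to 38% and power from 0% to 100%, driven by assumed priors, SD and trend; tighter priors tended to lose power and vaguer ones to give false success. The firm contrast is that the additive comparison does not depend on the placebo trend.

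A reader might go further and infer that the trial's type I error is at risk. It is not: these endpoints are outside the controlled family in Section 11.3.3, so only secondary estimates and their interpretation are affected.

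**What to change.** In Section 11.3.2.3, and in the matching synopsis sentence, specify for FVC % predicted and hand-held myometry:

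- a Bayesian repeated-measures model with visit means unrestricted in sign and an additive treatment difference at each visit;
- adjustment for the baseline value and age group (≤ 9, > 9 years), with stated priors;
- the Week 48 difference in mean change, with its 95% credible interval, as the reported result.

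The progression-model DRR may be kept as supportive. The dystrophin model in Section 11.3.2.1 already has free time-point means and additive effects, but each boy contributes one post-baseline value there, so within-patient correlation must be added.

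The cost is protocol and SAP wording only. These two endpoints leave the DRR scale, and there is a small efficiency loss if their decline is in fact proportional.

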11.3.2.4 Analysis of Open-label Treatment Period

Extensions to the BPM described above will be used to perform efficacy analyses of the extended follow-up in the OL Treatment Period.

11.3.3 Multiplicity considerations

The overall type I family-wise error rate for the primary and key secondary efficacy endpoint comparisons will be controlled at the one-sided, 2.5% error rate.

In the United States/Other regions, the dystrophin and NSAA efficacy analyses will be conducted as described in [Section 11.3.2](#). Simulations have demonstrated that the type I error rate is maintained across a range of parameterizations.

In the EU/Japan, the NSAA endpoint will be compared first and if the efficacy threshold is crossed, the dystrophin endpoint will be compared.

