Summaries of the posterior distribution for the treatment difference in dystrophin compared to placebo at each time point for each arm will be provided including the probability that each treatment is superior to placebo at each time point, $\Pr(\theta_{T,j} > 0)$, as well as mean and 95% credible intervals.

The dystrophin analysis will be supplemented with dystrophin data from the ongoing Open-label extension study to the Phase 1 trial (WVE-DMDX51-002). These results will be available at the time of the first dystrophin interim analysis.

Missing dystrophin data can result from intercurrent events which include discontinuation of the study and non-evaluable biopsies. Previous pivotal studies in DMD, including exon skipping therapies, have had low study discontinuation rates (e.g. 0.6% and 2.7%) so it is anticipated that missing data resulting from study discontinuation will be limited (^{57,58}). With the selected estimand, missing dystrophin results due to study discontinuation will be handled using baseline imputation. Non-evaluable dystrophin will be addressed using imputation under the assumption of missing-at-random (MAR). The regression method for monotone missing data will be used for the multiple imputation with baseline dystrophin as a covariate and imputation stratified by treatment arm.

There will be two interim dystrophin efficacy analyses and a final dystrophin efficacy analysis. The dystrophin treatment effects will be declared significant at the interim or final analyses using a gatekeeping strategy where the WVE-210201 4.5 mg/kg arm is assessed first and, if significant, the WVE-210201 3 mg/kg arm is assessed. To account for the three possible analyses of the dystrophin treatment effects, a Bonferroni-level adjustment will be applied. A one-sided, significance threshold of $1 - (0.025/3) = 0.991667$ will be used for the Bayesian posterior probability of superiority of each dose compared to placebo. If successful for WVE-

210210 4.5 mg/kg, the same threshold will be used for WVE-210210 3 mg/kg. Specifically, success will be declared for WVE-210201 4.5 mg/kg if

1. $\Pr(\theta_{2,1} > 0) > 0.991667$ at the first dystrophin interim analysis,
2. $\Pr(\theta_{2,2} > 0) > 0.991667$ at the second dystrophin interim analysis, or
3. $\Pr(\theta_{2,3} > 0) > 0.991667$ at the final dystrophin analysis.

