With this plan, the 12-week WVE-210201 4.5 mg/kg treatment effect is assessed at the first dystrophin interim analysis, the 22-week WVE-210201 4.5 mg/kg treatment effect is tested at the second dystrophin interim analysis and the 46-week WVE-210201 4.5 mg/kg treatment effect is tested at the final dystrophin interim analysis. Similar comparisons will be made for the WVE-210201 3 mg/kg treatment effect if the 4.5 mg/kg treatment effect is significant.

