11.5.1 Dystrophin Interim Analyses

Interim analyses of dystrophin will determine if efficacy is demonstrated prior to study conclusion and may allow for stopping randomization to the WVE-210201 3 mg/kg arm. The

first interim dystrophin analysis will compare dystrophin protein levels between WVE-210201 and placebo using the Week 12 open biopsies collected from up to the first 30 patients randomized. The second interim dystrophin analysis will compare dystrophin protein levels between WVE-210201 and placebo from approximately 40 patients with Week 22 open biopsies (collected from the 31st through 70th patient). The dystrophin interim analyses will be supplemented with dystrophin data from the ongoing OL extension study to the Phase 1 trial (WVE-DMDX51-002). A final analysis of dystrophin will occur when up to 80 patients (collected from the 71st through a maximum of the 150th patient) have Week 46 open biopsies. The significance thresholds for the dystrophin analyses are described in [Section 11.3.2.1](#). If the first or second interim dystrophin analysis results in a significant WVE-210201 treatment effect, randomized patients will continue to complete 48 weeks of follow-up to assess clinical outcomes and other endpoints.

Randomization to the WVE-210201 3 mg/kg treatment arm may be stopped based on the interim analysis of dystrophin. Specifically, randomization to the WVE-210201 3 mg/kg treatment arm will stop, if there is a high posterior probability that the high dose is effective, and the low dose is less efficacious of the high dose. The specific thresholds are included in the SAP.

If randomization to the 3 mg/kg treatment arm is stopped, patients originally randomized to the 3 mg/kg treatment arm will be transitioned to the WVE-210201 4.5 mg/kg treatment arm and all future patients will be randomized to WVE-210201 4.5 mg/kg or placebo at a 2:1 ratio. For clinical endpoint analyses, including the NSAA, patients originally randomized to the WVE-210201 3 mg/kg arm who transition to the WVE-210201 4.5 mg/kg treatment arm will not be included in WVE-210201 4.5 mg/kg treatment effect estimation.

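### For US/Other regions, Section 11.3.3 claims one-sided 2.5% family-wise control, but the written rules give dystrophin and NSAA 0.025 each with no order or split: about 4.9% at nominal levels

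*Combined protocol and SAP*

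**What the plan says.** Section 11.3.3 makes one claim for all regions: "The overall type I family-wise error rate for the primary and key secondary efficacy endpoint comparisons will be controlled at the one-sided, 2.5% error rate". The regions are then handled differently.

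- **EU/Japan** has an explicit order: "In the EU/Japan, the NSAA endpoint will be compared first and if the efficacy threshold is crossed, the dystrophin endpoint will be compared".
- **US/Other** has only a reference to Section 11.3.2, followed by: "Simulations have demonstrated that the type I error rate is maintained across a range of parameterizations".

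Section 11.3.2 contains these rules.

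- **Dystrophin, 4.5 mg/kg (11.3.2.1):** "To account for the three possible analyses of the dystrophin treatment effects, a Bonferroni-level adjustment will be applied". Each of the three analyses uses a posterior threshold of 0.991667, that is 1 − 0.025/3.
- **Dystrophin, 3 mg/kg (11.3.2.1):** "Similar comparisons will be made for the WVE-210201 3 mg/kg treatment effect if the 4.5 mg/kg treatment effect is significant". The threshold is the same.
- **NSAA (11.3.2.2):** success needs the posterior probability that the drug "slows the rate of NSAA progression is greater than 0.975". No dystrophin result is a condition. The section also calls the NSAA analysis independent of the dystrophin analysis. That may describe only the model, but it supplies no gate.

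The dystrophin interims can affect NSAA in two ways, and neither is an alpha rule. The study may be stopped if a futility boundary is crossed at the second interim (4.1.2). Also, the two doses are pooled for NSAA, but "if the randomization to the WVE-210201 3 mg/kg arm is stopped after an interim analysis", they are not pooled. Section 11.5.1 says that "randomization to the WVE-210201 3 mg/kg treatment arm will stop, if there is a high posterior probability that the high dose is effective". It adds a second condition, that 3 mg/kg looks weaker than 4.5 mg/kg, and leaves the thresholds to the SAP.

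**The concern.** The dystrophin adjustment covers repeated looks at dystrophin only. It leaves nothing in reserve for NSAA, which then takes a full 0.025 of its own. Two tests at 0.025 with no link between them do not share a 2.5% family-wise rate.

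In the US, an NSAA result after failed dystrophin, or next to a 3 mg/kg dystrophin claim, could be presented as error-controlled when no written rule makes it so. An order supplied after unblinding would carry little weight.

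The order must also deal with the lower dose. After 4.5 mg/kg dystrophin succeeds, 3 mg/kg dystrophin and NSAA are both open at full level. Placing NSAA behind 4.5 mg/kg dystrophin alone would therefore not close the family.

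**Working it through.** **Inputs.** Dystrophin: a = 0.025/3 = 0.008333 at each of three looks (11.3.2.1). NSAA: 1 − 0.975 = 0.025 (11.3.2.2). Each patient has one post-baseline biopsy (11.3.2.1), so the three looks use different patients and are independent if the open-label supplement is set aside. Every threshold is assumed to hold its nominal level.

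**The plan's own figures.** 1 − 0.025/3 = 0.991667, as stated. Dystrophin at 4.5 mg/kg alone: 1 − (1 − a)³ = 2.48%, consistent with 2.5%. NSAA alone: 2.5%.

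**Both endpoints, nothing effective, futility not credited.**

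1 − (1 − a)³ × 0.975 = 4.92%; the Bonferroni bound is 3a + 0.025 = 5.0%.

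With patient-level correlation r between the endpoints, and each look sharing only its own patients with the NSAA analysis:

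| r | −0.5 | 0 | 0.5 | 0.8 | 1 |
|---|---|---|---|---|---|
| Family-wise error | 4.97% | 4.92% | 4.75% | 4.56% | 4.37% |

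**Does the 3 mg/kg drop rule lower this?** The thresholds are not in the text, so two sets were assumed, firing in about 6% and 29% of null trials. The simulated error is 4.9% to 5.0% at r = 0, 4.8% to 5.0% at 0.5 and 4.7% to 4.8% at 0.8. NSAA's own error is 2.5% to 2.8%.

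**Does futility lower it enough?** Suppose the stop were enforced, ended all further testing, and fired in a share s of the null trials with no success at looks 1 and 2.

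- p₁₂ = 1 − (1 − a)² = 0.01660
- p₃ = 1 − (1 − a) × 0.975 = 0.03312
- error = p₁₂ + (1 − p₁₂)(1 − s)p₃

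This gives 3.9% at s = 0.3 and 3.3% at s = 0.5. It reaches 2.5% only at s ≈ 0.74.

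**Only 4.5 mg/kg dystrophin effective** (4% with SD 3%, from 11.1; 3 mg/kg dystrophin and NSAA null; r = 0; 9, 12 and 24 patients per arm, which is 30, 40 and 80 patients less 10% dropout, divided by three).

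- Effect at all looks, with the drop rule in force and a drop assumed to end later 3 mg/kg testing: about 3.3% to 3.7%. The assumed drop thresholds run from 0.80 (high dose beats placebo) with 0.5 (high beats low) up to 0.99 with 0.95.
- Effect at Week 46 only: about 3.5%.

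**The case against.** **The SAP may hold the missing rule.** Sections 11.5.1 and 11.5.2 leave several thresholds to a SAP that is not in the text reviewed. It could state a US order or a binding futility rule. This stands as a limit on what can be concluded. But for US multiplicity, 11.3.3 points to 11.3.2, not to the SAP, and 11.3.2 has no such rule.

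**A reader might infer that the trial's true error is 4.9%.** The documents do not support that. The tests are Bayesian. NSAA borrows historical controls, dystrophin is supplemented with open-label data, and both use imputation. Any of these could move the rate up or down. What can be said is that the written thresholds do not deliver 2.5% at their nominal levels.

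**The simulations may cover it.** The sentence gives no rate and no scenarios. It does not say whether the error is per endpoint or family-wise, or whether futility was credited. It neither confirms nor refutes the claim.

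**Primary and key secondary labels imply an order.** That is a conventional reading, and dystrophin 4.5 mg/kg first would bring the global-null error to about 2.5%. But the protocol writes out the order for EU/Japan and for the two doses. For US dystrophin and NSAA it does not, and labels alone are not a test rule.

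**A reader might infer that the secondary case also reaches 4.9%.** That would need 3 mg/kg testing to continue through all three looks. With the high dose effective early and the low dose null, the plan's own drop rule would usually end it. Under assumed thresholds of 0.95 and 0.8, it fires in about 84% of trials by the first look and 99% by the second.

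**Conclusion.** The concern holds. For US/Other, the one-sided 2.5% family-wise claim is not delivered by the rules that 11.3.3 refers to. At nominal thresholds, with optional futility not credited, the global-null error is about 4.9%, with a range of about 4.4% to 5.0% over correlations from 1 to −0.5. When only 4.5 mg/kg dystrophin works, it is about 3.3% to 3.7%, conditional on assumed drop thresholds and effect timing.

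This does not mean that the US primary claim is inflated: 4.5 mg/kg dystrophin taken alone stays near 2.5% nominally. The gap concerns the joint claim over primary and key secondary endpoints. The absence of a written rule in the protocol is certain; the actual error rate of the planned Bayesian tests is not known from the text.

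**What to change.** Write one US/Other rule in 11.3.3. If the SAP already holds one, state it there.

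**(a) Fixed sequence at the present thresholds**, starting with 4.5 mg/kg dystrophin (success at any look) and placing both remaining tests.

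- *4.5 mg/kg, NSAA, 3 mg/kg* removes interim 3 mg/kg dystrophin claims, because the final NSAA analysis waits for 48 weeks of follow-up in all randomized patients (11.5.2).
- *4.5 mg/kg, 3 mg/kg, NSAA* keeps those claims but makes NSAA wait on the 3 mg/kg result.
- Either way, say what happens to the 3 mg/kg step if randomization to that arm stops.
- Cost: NSAA depends on a surrogate. With the 4% effect at Week 46 only and 24 per arm, the 4.5 mg/kg gate has 98.1% power. It falls to 92.6% or 74.9% if early enrollment stopping leaves 60 or 40 patients in the Week 46 cohort (assumed sizes). At full enrollment and independence, NSAA directly after that gate has power 0.9815 × 0.8785 = 86% (45 v 45) or 0.9815 × 0.952 = 93% (45 v 90).

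**(b) Alpha split**, for example 0.0125 each: 0.995833 per dystrophin look (4.5 mg/kg, then 3 mg/kg) and 0.9875 for NSAA. Total: 1 − (1 − 0.0125/3)³ × 0.9875 = 2.48%. Power costs by t-test (NSAA difference 3, SD 4.5; dystrophin 4%, SD 3%):

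| Test | Present level | Split |
|---|---|---|
| NSAA, 45 v 45 (reproduces the plan's 88%) | 87.9% | 80.9% |
| NSAA, 45 v 90 pooled | 95.2% | 91.6% |
| Dystrophin Week 46, 24 v 24 | 98.1% | 96.4% |

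**(c) Otherwise restate the claim** as 2.5% nominal per endpoint, not controlled at 2.5% across both. This costs no power.

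In every case, report the simulated family-wise error by scenario without crediting non-binding futility. Include historical borrowing, the open-label supplement and the switch from pooled doses to 4.5 mg/kg only. The work is a short amendment to 11.3.3, matching SAP text and a simulation table; option (a) with NSAA second also changes the dose gatekeeping in 11.3.2.1.
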